Appendix 7 St. George's Respiratory Questionnaire (cont.)

St. George's Respiratory Questionnaire PART 2

Section 3

These are more questions about your cough and shortness of breath these days.

For each statement please check
(**the box** that applies
to you **these days**:

	True	False
Coughing hurts		
Coughing makes me tired		
I am short of breath when I talk		
I am short of breath when I bend over		
My coughing or breathing disturbs my sleep		
I get exhausted easily		

Section 4

These are questions about other effects that your respiratory problems may have on you these days.

For each statement, please
check (**the box** that
applies to you **these days**:

	True	False
My cough or breathing is embarrassing in public		
My respiratory problems are a nuisance to my family, friends or neighbors		
I get afraid or panic when I cannot catch my breath		
I feel that I am not in control of my respiratory problems		
I do not expect my respiratory problems to get any better		
I have become frail or an invalid because of my respiratory problems		
Exercise is not safe for me		
Everything seems too much of an effort		

Section 5

These are questions about your respiratory treatment. If you are not receiving treatment go to section 6.

For each statement, please
check (**the box** that applies
to you **these days**:

	True	False
My treatment does not help me very much		
I get embarrassed using my medication in public		
I have unpleasant side effects from my medication		
My treatment interferes with my life a lot		

USA / US English version

continued...

F:\institute\outadap\project\gsk1881\question\final_versions\sgqrusaq.doc 18/04/03

MSTT1041A—Genentech, Inc.
132/Protocol GB39242, Version 4

Clinical Study Report: RO7187807 - Genentech, Inc.
Protocol GB39242 Report Number 1097359

3304

Appendix 7 St. George's Respiratory Questionnaire (cont.)

St. George's Respiratory Questionnaire PART 2

Section 6

These are questions about how your activities might be affected by your respiratory problems.

For each statement, please check
the box that applies to you
because of your respiratory problems:

	True	False
I take a long time to get washed or dressed		
I cannot take a bath or shower, or I take a long time to do it		
I walk slower than other people my age, or I stop to rest		
Jobs such as household chores take a long time, or I have to stop to rest		
If I walk up one flight of stairs, I have to go slowly or stop		
If I hurry or walk fast, I have to stop or slow down		
My breathing makes it difficult to do things such as walk up hills, carry things up stairs, light gardening such as weeding, dance, bowl or play golf		
My breathing makes it difficult to do things such as carry heavy loads, dig in the garden or shovel snow, jog or walk briskly (5 miles per hour), play tennis or swim		
My breathing makes it difficult to do things such as very heavy manual work, ride a bike, run, swim fast, or play competitive sports		

Section 7

We would like to know how your respiratory problems usually affect your daily life.

For each statement, please check
the box that applies to you **because of**
your respiratory problems:

	True	False
I cannot play sports or do other physical activities		
I cannot go out for entertainment or recreation		
I cannot go out of the house to do the shopping		
I cannot do household chores		
I cannot move far from my bed or chair		

USA / US English version

continued...

f:\institut\cultadap\project\gsk1881\question\final_versions\sgrqusaq.doc 18/04/03

MSTT1041A—Genentech, Inc.
133/Protocol GB39242, Version 4

Clinical Study Report: RO7187807 - Genentech, Inc.
Protocol GB39242 Report Number 1097359

3305

Appendix 7 St. George's Respiratory Questionnaire (cont.)

St. George's Respiratory Questionnaire

Here is a list of other activities that your respiratory problems may prevent you from doing. (You do not have to check these, they are just to remind you of ways your shortness of breath may affect you):

- Going for walks or walking the dog
- Doing activities or chores at home or in the garden
- Sexual intercourse
- Going to a place of worship, or a place of entertainment
- Going out in bad weather or into smoky rooms
- Visiting family or friends or playing with children

Please write in any other important activities that your respiratory problems may stop you from doing:

.....

.....

.....

.....

Now please check the box (one only) that you think best describes how your respiratory problems affect you:

- It does not stop me from doing anything I would like to do
- It stops me from doing one or two things I would like to do
- It stops me from doing most of the things I would like to do
- It stops me from doing everything I would like to do

Thank you for completing this questionnaire. Before you finish would you please make sure that you have answered all the questions.

USA / US English version

f:\institut\cutadap\project\gsk1881\question\final_versions\legqrqsaq.doc 18/04/03

MSTT1041A—Genentech, Inc.
134/Protocol GB39242, Version 4

Clinical Study Report: RO7187807 - Genentech, Inc.
Protocol GB39242 Report Number 1097359

Appendix 8 Clinician Global Impression of Change

Clinician Global Impression of Change (CGIC)

How would you rate the change in the subject's asthma symptoms since they started taking the study drug?

- Very much improved
- Much improved
- Minimally improved
- No change
- Minimally worse
- Much worse
- Very much worse

Appendix 9 Patient Global Impression of Change

Patient Global Impression of Change (PGIC)

How would you rate the change in your asthma symptoms since starting the study drug?

- Very much improved
- Much improved
- Minimally improved
- No change
- Minimally worse
- Much worse
- Very much worse

Appendix 10 EuroQol 5-Dimension Questionnaire (EQ-5D-5L)

Health Questionnaire

English version for the USA

USA (English) © 2009 EuroQol Group EQ-5D™ is a trade mark of the EuroQol Group

MSTT1041A—Genentech, Inc.
137/Protocol GB39242, Version 4

Clinical Study Report: RO7187807 - Genentech, Inc.
Protocol GB39242 Report Number 1097359

Appendix 10 EuroQol 5-Dimension Questionnaire (cont.)

Under each heading, please check the ONE box that best describes your health TODAY.

MOBILITY

- I have no problems walking
- I have slight problems walking
- I have moderate problems walking
- I have severe problems walking
- I am unable to walk

SELF-CARE

- I have no problems washing or dressing myself
- I have slight problems washing or dressing myself
- I have moderate problems washing or dressing myself
- I have severe problems washing or dressing myself
- I am unable to wash or dress myself

USUAL ACTIVITIES (e.g. work, study, housework, family or leisure activities)

- I have no problems doing my usual activities
- I have slight problems doing my usual activities
- I have moderate problems doing my usual activities
- I have severe problems doing my usual activities
- I am unable to do my usual activities

PAIN / DISCOMFORT

- I have no pain or discomfort
- I have slight pain or discomfort
- I have moderate pain or discomfort
- I have severe pain or discomfort
- I have extreme pain or discomfort

ANXIETY / DEPRESSION

- I am not anxious or depressed
- I am slightly anxious or depressed
- I am moderately anxious or depressed
- I am severely anxious or depressed
- I am extremely anxious or depressed

USA (English) © 2009 EuroQol Group EQ-5D™ is a trade mark of the EuroQol Group

[figure not shown]
MSTT1041A—Genentech, Inc.
138/Protocol GB39242, Version 4

Clinical Study Report: RO7187807 - Genentech, Inc.
Protocol GB39242 Report Number 1097359

Appendix 10 EuroQol 5-Dimension Questionnaire (cont.)

- We would like to know how good or bad your health is TODAY.
- This scale is numbered from 0 to 100.
- 100 means the best health you can imagine.
0 means the worst health you can imagine.
- Mark an X on the scale to indicate how your health is TODAY.
- Now, please write the number you marked on the scale in the box below.

YOUR HEALTH TODAY =

USA (English) © 2009 EuroQol Group EQ-5D™ is a trade mark of the EuroQol Group

Appendix 11 Compliance With Asthma Controller Medication

[Included in evening daily from screening through Week 54]

Did you take your preventive inhaler (medications) today?

Yes

No

Appendix 12

Definition of Asthma Exacerbation for Inclusion Criteria and Reporting of Adverse Events

Asthma exacerbation is defined as new or increased asthma symptoms (wheezing, coughing, dyspnea, chest tightness, and/or nighttime awakenings due to these symptoms) that result in one or both of the following:

- Hospitalization or emergency department, urgent care visit or urgent unscheduled office visit requiring administration of asthma treatment, such as bronchodilators and/or systemic corticosteroids, in addition to baseline controller medications
- Treatment with systemic corticosteroids for ≥ 3 days or a long-acting depot corticosteroid preparation with a therapeutic effectiveness of ≥ 3 days

Severe asthma exacerbation is defined as asthma symptoms requiring hospitalization or resulting in death attributed to asthma.

1. BACKGROUND

The purpose of this document is to provide details of the planned analyses for Study GB39242. The primary focus of this Statistical Analysis Plan (SAP) is on analyses of complete data from the first 54 weeks of the study, which includes the 2-week single-blind placebo run-in as well as the 52-week double-blind treatment period. Such analyses are described in the main body of this document and will be performed after all patients have completed 54 weeks in the study or discontinued early, and all corresponding data have been entered into the database, reviewed, and verified. The 16-week follow-up period of the study may be ongoing at the time of the 54-week analysis. No changes to the SAP will be allowed at the time of or subsequent to the 54-week primary analysis.

The analyses specified in this document supersede the high-level analysis plan described in the protocol.

2. STUDY DESIGN

Study GB39242 is a Phase IIb, randomized, placebo-controlled, double-blind, multicenter, multi-arm study of MSTT1041A compared with placebo as add-on therapy in patients with severe, uncontrolled asthma who are receiving medium- or high-dose inhaled corticosteroids (ICS) therapy and at least one of the following additional controller medications: long-acting β -agonist, leukotriene modifier, long-acting muscarinic antagonist, or long-acting theophylline preparation. Patients must have evidence of uncontrolled disease consisting of an Asthma Control Questionnaire-five items (ACQ-5) score of ≥ 1.5 and at least one symptom of asthma that is not controlled (nighttime awakening ≥ 1 time/week and/or short-acting rescue therapy use > 2 days/week). Patients requiring use of systemic corticosteroids (oral, intravenous, or intramuscular) or biologic therapy (e.g., anti-Immunoglobulin E [IgE] or anti-interleukin-5) at screening were excluded from the study.

The study consists of a 2- to 4-week screening period, a 2-week single-blind placebo run-in period, a 52-week double-blind treatment period, and a 16-week safety follow-up period concluding with the end-of-study visit at Week 70 (see [Figure 1](#)). At the run-in visit (Week 0), scheduled for approximately 2 weeks prior to the randomization visit (Week 2), patients who met enrollment criteria for the run-in period received one single-blind dose of placebo to allow for evaluation of unexpected variability in asthma control. At the randomization visit, patients underwent further assessments to determine eligibility for randomization to the double-blind treatment period. The 52-week double-blind treatment period begins with the randomization visit (Week 2) and ends with the Week 54 visit. Patients who experienced unexpected variability in asthma control during the run-in period, as demonstrated by change in forced expiratory volume in 1 second (FEV₁) and/or fractional exhaled nitric oxide (FeNO), were not eligible for

randomization into the 52-week double-blind treatment period. Additional details are provided in the study protocol.

Eligible patients were randomized in a 1:1:1:1 ratio to receive MSTT1041A at one of three doses (70, 210, or 490 mg) or placebo. Enrollment caps were utilized to ensure adequate power for biomarker subgroup analysis based upon blood eosinophil status at visit 1 (≥ 300 , < 300 cells/ μ L). The randomization was conducted such that approximately 30 patients per arm will have eosinophil-high status and approximately 95 patients per arm will have eosinophil-low status. Study drug is administered as four SC abdominal injections at the randomization visit (Week 2), Week 6, and every 4 weeks thereafter through Week 50.

[figure not shown]
Safety and efficacy, as well as pharmacokinetic (PK) and pharmacodynamic (PD) measures, are assessed throughout the double-blind treatment period, as described in the protocol and detailed in the Schedule of Assessments (see [Appendix 2](#)). The primary efficacy endpoint is the incidence of asthma exacerbations during the 52-week double-blind treatment period (Week 2 through Week 54).

All patients will be followed for 20 weeks after the last dose of study treatment. The 20 weeks include 4 weeks after the final dose in the double-blind treatment period and 16 weeks in the safety follow-up period. Assessments for the safety follow-up period are detailed in the Schedule of Assessments (see [Appendix 2](#)).

All patients who discontinue study drug early during the double-blind treatment period are asked to continue with the study assessments in the double-blind treatment period and then complete the safety follow-up period. Patients who are unable or unwilling to continue with assessments in the double-blind treatment period complete an early termination visit and then enter the safety follow-up period.

The study design is depicted in [Figure 1](#).

Figure 1 Study Schema

ICS=inhaled corticosteroid; Q4W=every 4 weeks; SC=subcutaneous.

2.1 OUTCOME MEASURES

2.1.1 Primary Efficacy Endpoint

The primary efficacy endpoint is as follows:

- Incidence of asthma exacerbations from baseline through Week 54, with asthma exacerbation defined as new or increased asthma symptoms (wheezing, coughing, dyspnea, chest tightness, and/or nighttime awakenings due to these symptoms) that result in one or both of the following:
 - Hospitalization or an emergency department visit with administration of systemic corticosteroids treatment
 - Treatment of systemic corticosteroids for ≥ 3 days or a long-acting depot corticosteroid preparation with a therapeutic effectiveness of ≥ 3 days

2.1.2 Secondary Efficacy Endpoints

The secondary efficacy endpoints are as follows:

- Absolute change in pre-bronchodilator FEV₁ (liters) from baseline to Week 54
- Time to first asthma exacerbation during the 52-week double-blind treatment period
- Achievement of improvement Standardized Asthma Quality-of-Life Questionnaires (AQLQS) score, defined as an increase of ≥ 0.5 points from baseline to Week 54
- Achievement of improvement in ACQ-5 score at Week 54, defined as a decrease of ≥ 0.5 points from baseline to Week 54
- Absolute change in patient-reported use of short-acting rescue therapy from baseline to Week 54

- Proportion of weeks without patient-reported asthma-related nighttime awakenings from baseline through Week 54
- Absolute change in patient-reported daytime asthma symptom severity as measured by the Asthma Daily Symptom Diary (ADSD) from baseline to Week 54

2.1.3 Exploratory Efficacy Endpoints

The exploratory efficacy endpoints are as follows:

- Incidence of asthma exacerbations from baseline through Week 54, with asthma exacerbation defined as in [Appendix 5](#)
- Incidence of severe asthma exacerbations from baseline through Week 54, with severe asthma exacerbation defined as asthma symptoms requiring hospitalization or resulting in death attributed to asthma
- Incidence of asthma exacerbations from randomization visit through Week 70
- Relative change in pre-bronchodilator FEV₁ (liters) from baseline to Week 54
- Absolute change in pre-bronchodilator FEV₁ (percentage predicted) from baseline to Week 54
- Absolute change in pre-bronchodilator FEV₁ (liters) from baseline to Week 70
- Achievement of improvement in St. George's Respiratory Questionnaire (SGRQ) score, defined as a decrease of ≥ 4 points from baseline to Week 54
- Achievement of improvement in ACQ-7 score, defined as a decrease of ≥ 0.5 points from baseline to Week 54
- Clinician's global impression of change (CGIC) in patient's asthma symptoms, as assessed through use of the CGIC, from baseline to Week 26 and Week 54
- Incidence of asthma exacerbations from baseline through Week 54 within each of the eosinophil-high (≥ 300 cells/ μ L) and eosinophil-low (< 300 cells/ μ L) groups
- Absolute change from baseline to Week 54 in pre-bronchodilator FEV₁ (liters) within each of the eosinophil-high (≥ 300 cells/ μ L) and eosinophil-low (< 300 cells/ μ L) groups
- Incidence of asthma exacerbations from baseline through Week 54 by *IL1RL1* genotype
- Absolute change in pre-bronchodilator FEV₁ (liters) from baseline to Week 54 by *IL1RL1* genotype

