3. STUDY DESIGN

3.1 DESCRIPTION OF THE STUDY

3.1.1 Overview of Study Design

This is a Phase IIb, randomized, placebo-controlled, double-blind, multicenter, multi-arm study of MSTT1041A compared with placebo as add-on therapy in patients with severe, uncontrolled asthma who are receiving medium- or high-dose ICS therapy and at least one of the following additional controller medications: LABA, leukotriene modifier (LTM), long-acting muscarinic antagonist (LAMA), or long-acting theophylline preparation. Patients must have evidence of uncontrolled disease consisting of an Asthma Control Questionnaire–five items (ACQ-5) score of ≥ 1.5 and at least one symptom of asthma that is not controlled *during each of 2 consecutive weeks* (nighttime awakening ≥ 1 time/week and/or short-acting rescue therapy use > 2 days/week). Patients requiring use of systemic corticosteroids (oral, IV, or intramuscular [IM]) or biologic therapy (e.g., anti-IgE or anti-IL-5) at screening will be excluded from the study.

The study will consist of a 2- to 4-week screening period, a 2-week single-blind placebo run-in period, a 52-week double-blind treatment period, and a 16-week follow-up period concluding at the end-of-study (EOS) visit at Week 70.

At screening, patients must demonstrate acceptable inhaler, peak flow meter, and spirometry techniques. During the screening period, patients must demonstrate compliance with required daily use of an electronic device (eDiary) for documenting asthma controller medication use and answering questions related to asthma symptoms, nighttime awakenings due to asthma, and use of short-acting rescue therapy; compliance with daily measurement of peak expiratory flow rate (PEFR); and adherence to their usual asthma controller medication regimen (ICS plus at least one additional controller medication), as recorded daily in the eDiary (see Section 4.1.1 for details).

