4.4.4 Asthma Therapy and Concomitant Therapy Restrictions

Asthma therapy and concomitant therapy restrictions are summarized in Table 2.

Table 2 Asthma Therapy and Concomitant Therapy Restrictions

Medication	Restrictions ^a
ICS therapy	On a stable regimen for ≥ 3 months prior to screening, with no changes within 4 weeks prior to screening, during the screening or run-in periods, or during the treatment period
LABA therapy LTMs LAMA therapy	No changes in dose or initiation of therapy within 4 weeks prior to screening, during the screening or run-in periods, or during the treatment period
Long-acting theophylline preparations	No changes in dose or initiation of therapy within 4 weeks prior to screening, during the screening or run-in periods, or during the treatment period, except for dose adjustments as appropriate on the basis of serum theophylline levels
Allergen immunotherapy	No changes in dose or initiation of therapy within 3 months prior to screening, during the screening or run-in periods, or during the treatment period Must not be administered on the same day as study drug
Maintenance oral corticosteroids (daily or every other day)	Prohibited within 3 months prior to screening
Systemic corticosteroids (oral, IV, or IM)	Prohibited within 4 weeks prior to screening and during the screening and run-in periods Prohibited for treatment of any condition other than asthma exacerbations during the 52-week double-blind treatment period
Intra-articular corticosteroids Phosphodiesterase-4 inhibitors (e.g., roflumilast) Live or live, attenuated vaccines Immunoglobulin or blood products	Prohibited within 4 weeks prior to screening, during the screening and run-in periods, and during the 52-week double-blind treatment period

Table 2 Asthma Therapy and Concomitant Therapy Restrictions (cont.)

Medication	Restrictions ^a
Maintenance oral and SC β -agonist therapy (e.g., terbutaline)	Prohibited within 2 weeks prior to screening, during the screening and run-in periods, and during the 52-week, double-blind, treatment period
Investigational therapy, including investigational use of a formulation of an approved drug ^b	Prohibited within 3 months or 5 drug half-lives prior to screening (whichever is longer), during the screening and run-in periods, and during the 52-week, double-blind treatment period

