Licensed biologic agents (e.g., omalizumab, mepolizumab, suplatast)	Prohibited within 3 months or 5 drug half-lives prior to screening (whichever is longer), during the screening and run-in periods, and during the 52-week, double-blind treatment period
Immunomodulatory, immunosuppressive, or experimental anti-inflammatory therapy other than biologic agents or corticosteroids (see separate exclusions above)	Prohibited within 3 months or 5 drug half-lives prior to screening (whichever is longer), during the screening and run-in periods, and during the 52-week, double-blind treatment period
Maintenance oral or inhaled antibiotics β -blocking agents (topical, oral, or other systemic) Homeopathic medications, herbal medications, acupuncture, or hypnosis therapy Maintenance intermittent positive pressure ventilation physiotherapy Maintenance bilevel positive airway pressure therapy	Prohibited within 2 weeks prior to screening, during the screening and run-in periods, and during the 52-week double-blind treatment period
Bronchial thermoplasty	Prohibited within 24 months prior to screening, during the screening and run-in periods, and during the 52-week, double-blind, treatment period
Pulmonary rehabilitation	Prohibited except on an outpatient basis for patients who have been participating for ≥ 6 months prior to screening and will continue to participate during the 52-week, double-blind, treatment period

ICS = inhaled corticosteroid; IM = intramuscular; IV = intravenous; LABA = long-acting β -agonist; LAMA = long-acting muscarinic antagonist; LTM = leukotriene modifier; SC = subcutaneous.

^a The Medical Monitor should be consulted in cases of uncertainty.

^b Patients participating in a clinical trial that has not been unblinded should be assumed to have received the active drug.

Patients who take any prohibited concomitant medications should not necessarily be withdrawn from the study or discontinue study treatment, as described in Section 4.6. The Medical Monitor should be consulted to ensure that there are no safety risks associated with continuing study drug or if a study treatment interruption should be considered.

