4.5.3 Exploratory Efficacy Endpoints

Asthma Exacerbation as Defined in Appendix 5

The incidence of asthma exacerbations, defined as in [Appendix 5](#), will be analyzed with the use of the same methodology as described for the primary endpoint (see Section 4.5.1).

Severe Asthma Exacerbations

The incidence of severe asthma exacerbations, defined as asthma symptoms requiring hospitalization or resulting in death attributed to asthma, will be analyzed with the use of the same methodology as described for the primary endpoint (see Section 4.5.1).

Asthma Exacerbations through Week 70

The incidence of severe asthma exacerbations from randomization through Week 70 will be analyzed with the use of the same methodology as described for the primary endpoint (see Section 4.5.1).

Relative Change in Pre-Bronchodilator Forced Expiratory Volume in 1 Second (Liters)

For each patient and timepoint, the relative change in pre-bronchodilator FEV₁ will be defined as the absolute change from the baseline in FEV₁ (liters) divided by the FEV₁ (liters) at baseline. The relative change in pre-bronchodilator FEV₁ from the baseline will be analyzed using the same methodology as described for the secondary endpoint of absolute change in pre-bronchodilator FEV₁ from baseline to Week 54, except that relative change from baseline will be the response variable.

Pre-Bronchodilator Forced Expiratory Volume in 1 Second (Percentage Predicted)

The absolute change in pre-bronchodilator FEV₁ (percentage predicted) from baseline to Week 54 will be analyzed using the same methodology as described for the secondary endpoint of absolute change in pre-bronchodilator FEV₁ from baseline to Week 54.

Pre-Bronchodilator Forced Expiratory Volume in 1 Second (Liters) at Week 70

The absolute change in pre-bronchodilator FEV₁ from baseline to Week 70 will be analyzed using the same methodology as described for the secondary endpoint of absolute change in pre-bronchodilator FEV₁ from baseline to Week 54.

St. George's Respiratory Questionnaire

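### The Week 70 exacerbation analysis gives one rate ratio over 52 double-blind and 16 follow-up weeks, so it cannot show what happens after dosing stops; its event definition and time at risk also need settling

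*SAP*

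**What the plan says.** **Endpoint.** SAP 2.1.3 lists "Incidence of asthma exacerbations from randomization visit through Week 70". Protocol Sections 2 and 6.4.3 also list all exacerbations through Week 70.

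**Analysis.** SAP 4.5.3 says the events "from randomization through Week 70 will be analyzed with the use of the same methodology as described for the primary endpoint". The subject of that sentence is *severe* asthma exacerbations, although the sub-heading above it does not say severe. The primary method (SAP 4.5.1) is a Poisson model with over-dispersion. It has three treatment indicators, the baseline covariates and an offset for time at risk. There is no period term and no treatment-by-period term. For completers, time at risk stops at the actual Week 54 visit.

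**Design.** Protocol 3.1.1 describes "a 52-week double-blind treatment period, and a 16-week follow-up period concluding at the end-of-study (EOS) visit at Week 70". Study drug is given "at the randomization visit (Week 2), Week 6, and every 4 weeks thereafter through Week 50" (SAP 2). Of the time after the last dose, "The 20 weeks include 4 weeks after the final dose in the double-blind treatment period and 16 weeks in the safety follow-up period".

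**Other conditions around Week 54.** In Protocol Table 2, biologic, investigational and immunomodulatory therapies are barred "during the screening and run-in periods, and during the 52-week, double-blind treatment period". Systemic corticosteroids are "Prohibited for treatment of any condition other than asthma exacerbations during the 52-week double-blind treatment period". Controller changes are restricted "during the screening or run-in periods, or during the treatment period". The schedule of activities has 14 post-randomization visits up to Week 54, then two (Weeks 62 and 70, each ±14 days). The eDiary is retrieved at Week 54.

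**Status.** Exploratory endpoints carry no type I error control (SAP 4.5). Sponsor analysts are unblinded at the Week 54 analysis (SAP 2.3), and the SAP may not be changed at or after that point (SAP 1).

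**The concern.** The 52-week rate is already the primary endpoint. What the Week 70 endpoint adds is the 16 weeks after dosing: whether the effect lasts, fades or reverses. A single ratio over 68 weeks answers a different question, because 52/68 = 76% of its planned time is the year already reported. Quite different off-treatment courses can all appear as a pooled ratio below 1. No other planned analysis gives an exacerbation rate ratio for Weeks 54–70.

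The analysis text also cannot be programmed without a decision. It names a different event from the endpoint list, and it borrows a risk window that closes 16 weeks too early.

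**Working it through.** **Inputs from the documents.** 52 and 16 weeks (Protocol 3.1.1); 125 patients per arm (Protocol 4.1); placebo rate 0.63 per patient-year, 40% reduction (ratio 0.60), no over-dispersion, 15% dropout, two-sided 0.05 (SAP 2.2).

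**Assumptions, not in the documents.** The Week 54–70 rate ratio *r*, varied from 0.60 to 2.0, and the same placebo rate in both periods.

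**The plan's own figure.** There is none for Week 70. The stated power of about 80% for 52 weeks comes back as 79.3% to 80.8% (Wald, square-root and rate-difference tests) only when dropout is ignored. It is 72.6% to 74.2% if dropouts contribute no time. That gap is a separate matter, but it is why results below are given with and without dropout.

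**Pooled ratio.** (52 × 0.60 + 16 × *r*) / 68:

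| Follow-up ratio *r* | Calculation | Pooled ratio |
|---|---|---|
| 0.60 (effect persists) | (31.2 + 9.6)/68 | 0.600 |
| 0.80 | (31.2 + 12.8)/68 | 0.647 |
| 1.0 (effect gone) | (31.2 + 16)/68 | 0.694 |
| 1.5 | (31.2 + 24)/68 | 0.812 |
| 2.0 | (31.2 + 32)/68 | 0.929 |

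The pooled ratio reaches 1 when *r* = (68 − 31.2)/16 = 2.30.

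**Precision of a separate Week 54–70 estimate.**
- Expected placebo events: 125 × 0.63 × (16 × 7/365.25) = 24.1. With 15% dropout: 24.1 × 0.85 = 20.5.
- 95% CI factor at a ratio of 1, one dose against placebo: exp(1.96 × √(2/24.1)) = 1.76. With dropout: exp(1.96 × √(2/20.5)) = 1.84.
- All doses combined against placebo: exp(1.96 × √(1/24.1 + 1/72.3)) = 1.59.
- For a true ratio of 1.5 (24.1 against 36.2 events): 95% CI 0.90 to 2.51, power 34% (30% with dropout). For 2.0: power 79% (73%).

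These counts use the 0.63 rate and so apply to all protocol-defined exacerbations. If *severe* were intended (hospitalization or asthma death), 0.63 would not apply and the counts would need another source. Over-dispersion would widen every interval.

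**The case against.** A reader might infer several stronger points. The documents do not support them.

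- **That pooling dilutes the drug effect.** This needs the effect to wane. The readable text gives no half-life or offset data, and part of the dose rationale is redacted. If the effect persists, the pooled ratio stays 0.60 and power rises to 88.7% without dropout, against 79.3% for 52 weeks on the same Wald test.
- **That the model is invalid because it assumes a constant ratio.** With similar follow-up across arms, a Poisson count model with an offset estimates the ratio of average rates over the window. That summary is legitimate; it is only uninformative about timing.
- **That a rebound would go unseen.** The Week 54 result stands separately, so a rough subtraction is possible: (68 × pooled − 52 × 0.60)/16. FEV₁ at Week 70 comes from a model with visit-specific estimates. Exacerbations are also reported as adverse events until at least 20 weeks after the last dose. But subtraction yields no adjusted ratio or valid interval, and none of the other sources is an exacerbation rate ratio.
- **That controller restrictions end at Week 54.** Table 2 stops at the treatment period, but Protocol 4.4.1 expects no dosing changes throughout the study and says changes should be avoided, with no end date.
- **That endpoint events are lost with the eDiary.** The diary records symptoms, awakenings, rescue use and controller use, not corticosteroid courses or hospital visits. Exacerbations are asked about at each visit and have their own eCRF. Patients and sites stay blinded, so differential under-reporting is not expected. The longer recall interval remains, at about 8 weeks rather than 2 to 4.

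Two objections to a separate analysis also stand. It includes only patients still followed after Week 54, which weakens the randomized comparison. It also does not isolate stopping, since early discontinuers may be off drug well before Week 54. Both argue for a descriptive label, not for omitting the analysis.

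**Conclusion.** The point holds as a limited gap in an exploratory analysis. The planned ratio cannot distinguish persistence, loss of effect and rebound: with 0.60 over 52 weeks, follow-up ratios of 0.60, 1.0 and 1.5 give 0.60, 0.69 and 0.81, all below 1, and the sign changes only above about 2.3. This rests on assumed follow-up ratios and equal background rates. It shows what the summary could conceal, not what will occur.

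Two textual defects need no assumption: *severe* in SAP 4.5.3 against all exacerbations in 2.1.3, and a time at risk that closes at Week 54 for an endpoint running to Week 70. The primary result is not touched, and nothing here shows that the Week 70 ratio would be biased or the drug effect understated.

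**What to change.** Amend SAP 4.5.3 before the Week 54 analysis, after which the SAP is closed and the analysts are unblinded:

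1. Reconcile *severe* with the endpoint list in 2.1.3.
2. Define time at risk for this endpoint from randomization to the Week 70 visit, or to the last assessment for patients who leave earlier.
3. Beside the 68-week result, report rates and rate ratios with 95% CIs for exacerbations with onset after the Week 54 visit through Week 70, for each dose and for all doses combined. Use the same model, with that period's time at risk as the offset.
4. Tabulate by arm the patients who start a Table 2 restricted therapy in follow-up. Table 2 and Protocol 4.4.1 must be reconciled on controller changes before those are classified.
5. Label the Week 54–70 results descriptive, and state that they cover only patients still followed after Week 54.

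The cost is one further model and one table. Exacerbations and medications are already recorded to the end-of-study visit. The price is imprecision: a CI factor of 1.76 to 1.84 per dose and 30% to 34% power for a ratio of 1.5. A wide interval around 1 should therefore not be read as absence of rebound.
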